6.1.1. Screening

Written informed consent for the study will be obtained prior to the performance of any study-related procedures including screening procedures. A 3-week period is provided for completing screening assessments and determining subject eligibility for the study. Safety labs may be re-tested up to 2 additional times for determination of subject eligibility after consultation with the Sponsor Medical Monitor.

During the Screening Period, subjects will undergo a medical history (including cardiovascular disease risk factors) and physical examination including vital signs, orthostatic hypotension assessment, 12-lead ECG, and have blood and urine samples taken for clinical laboratory testing. Subjects will be screened for HIV, HepB, and HCV.

The study site will record basic personal details about the subject, including the subject's name, contact details, gender, height, weight, date of birth, age, ethnicity, and racial origin (to be used only for clinical purposes), as well as information on the subject's medical history, and clinical data collected about the subject's participation in the study.

6.1.1.1. Seated Blood Pressure Measuring Instructions at Each Visit

Subject Instructions:

- Subject should be wearing a loose, short-sleeved top. If patient is wearing a long-sleeved or tight garment around the arm, provide a gown or remove the arm from the sleeve
- Subject should be comfortably seated (e.g., with his/her back against the chair, feet flat on the floor)
- Subject's arm should be bent at the elbow and supported by a table

Observer Instructions:

- Place the cuff on the subject's upper arm at the level of the heart and centered at the midpoint of the humerus
- Leave patient alone for 5 minutes in a quiet setting
- After 5 mins, return and take 3 readings, with 60 seconds between readings
- Document the average of the 3 readings

BP Results:

- At the screening visit, measure the BP per instructions above with both the right and left arm. The arm with the highest BP (that meets inclusion/exclusion criteria) will be used at each subsequent visit and during the 3 times a week at-home BPM

6.1.1.2. Orthostatic Blood Pressure Assessment

An orthostatic BP assessment will be done at Screening. Blood pressure and pulse rate will be assessed 2 times (Table 2). The patient will lie down (supine) for at least 5 minutes, then BP and pulse rate will be measured. The patient will then change to a standing position and the BP and

pulse rate measurements will be repeated after standing greater than one minute, but less than or equal to 3 minutes.

Borderline orthostatic hypotension will be defined as a confirmed (sequence must be repeated to confirm) decrease in SBP ≥ 17 mmHg and/or a decrease in DBP of ≥ 7 mmHg from BP at supine position. During the study, orthostatic hypotension will be defined as a confirmed (sequence must be repeated to confirm) decrease in SBP of ≥ 20 mmHg and/or a decrease in DBP of ≥ 10 mmHg after standing greater than 1 minute, but less than or equal to 3 minutes. The diagnosis will be made specific to each visit with no comparison to Baseline (Study Day 1 pre-dose) values.

Table 2: Orthostatic Hypotension Assessment

Position	Time in Position	Vital Signs Assessed
Supine	5 minutes	Blood Pressure and Pulse Rate after 5 minutes
Standing	> 1 to ≤ 3 minutes	Blood Pressure and Pulse Rate assessed within > 1 to ≤ 3 minutes of standing

6.1.1.3. At Home Blood Pressure and Heart Rate Monitoring

Subjects will be provided with a study BPM kit. Subjects will be required to measure their BP and HR at approximately the same time in the morning 3 times a week throughout the study (up to 1 missed BP and HR every 7 days is allowed). Three (3) at home BP and HR measurements should be taken every 7 calendar days on non-sequential days no more than 2 calendar days apart (e.g., Monday, Thursday, Saturday). During the assessments, subjects will first rest in a quiet setting for 5 minutes and then evaluate BP and HR in triplicate each time, with 60 seconds between each measurement and then record the average value. All subjects will be trained by the clinic staff and provided written instructions on how to use the BPM kit. Subjects will contact the Investigator if BP results meet the criteria as outlined in the Safety Monitoring Rules for Blood Pressure and Stopping Rules for Blood Pressure outlined in Section 8.

6.1.2. Run-In Period

The Run-In Period will be 1 week, and subjects will conduct thrice weekly at home evaluations for vital signs (e.g., BP, HR) and will be assessed for compliance with their antihypertensive medications. Subjects who do not complete the Run-In Period or do not continue to meet the eligibility criteria will be considered a screen failure.

6.1.3. Washout Period

The WO Period will be 2 weeks and subjects will stop all of their antihypertensive medications at the beginning and conduct thrice weekly evaluations for vital signs (e.g., BP, HR) at home. Vital signs will be performed on Study Day -14 at the clinic.

On Weeks -2 and -1 subjects will return to the clinic for study assessments outlined in [Appendix A](#). Subject vital signs and safety assessments will be conducted to confirm eligibility

on Week -1 (Study Day -7). Subjects who do not complete the WO Period or do not continue to meet the eligibility criteria will be considered a screen failure.

6.1.4. Treatment Period

Eligible subjects will be administered Study Drug (ISIS 757456 or placebo) on a weekly basis (6 weeks) as well as an additional dose on Study Day 3 for a total of 7 doses. Review of the at-home blood pressures and the in-clinic BP should be performed prior to administering the Study Drug.

Safety and clinical laboratory evaluations as well as blood sampling for PK analysis will be performed periodically throughout the Treatment Period ([Appendix A](#), [Appendix B](#), and [Appendix C](#)). Any AEs and concomitant medications will be recorded. If antihypertensive medications are re-instated this will be captured in the concomitant medications eCRF. All safety data including AEs, at home and in-clinic BP, and concomitant medications will be reviewed by the Sponsor's Medical Monitor or designee on an ongoing basis throughout the trial.

Subjects will continue at home BP and HR monitoring during the Treatment Period as outlined in Section [6.1.1.3](#) and [Appendix A](#). Subjects who discontinue the Treatment Period early will continue in the study following the post-treatment evaluations (Section [6.1.5](#))

6.1.5. Post-Treatment Evaluation Period

After the last dose (Study Day 36) or last dose for early termination subjects, subjects will return to the clinic once-weekly for the first 2 weeks (Study Days 43, 50) and then on Study Days 64, 78, 106, and 127 for safety assessments.

Subjects will continue at home BP and HR monitoring during the Post-Treatment Period as outlined in Section [6.1.1.3](#) and [Appendix A](#).

All safety data including AEs, at home and in-clinic BP, and concomitant medications will be reviewed by the Sponsor's Medical Monitor or designee on an ongoing basis throughout the trial.

6.2. Laboratory Assessments

Laboratory analyte samples will be collected throughout the study. A list of these analytes is contained in [Appendix B](#). Blood chemistry should be taken after fasting for at least 8 hours. During this time the patient can drink water and they should ensure that they consume sufficient water in order to not become dehydrated.

If the platelet value, serum creatinine or liver enzyme tests are uninterpretable (e.g., due to clumping, hemolysis or quantity not sufficient) or missing a repeat blood specimen should be re-drawn as soon as possible (ideally within 7 days). Due to time constraints, a local lab draw is recommended if a repeat blood specimen is necessary to continue dosing at any time after Study Day 1 to Study Day 8. If there is suspicion of EDTA mediated platelet clumping, a repeat platelet count should be collected in a sodium citrate tube as soon as possible.

6.3. Restriction on the Lifestyle of Subjects

6.3.1. Contraception Requirements

All male subjects must refrain from sperm donation and either be abstinent[†] or use highly effective contraception from the time of signing the informed consent form until at least 13 weeks after their last dose of study treatment.

For male subjects engaged in sexual relations with a WOCBP either the subject or their female partner must use highly effective contraception from the time of signing the informed consent until 13 weeks after the subject's last dose of study treatment.

For the purposes of this study, WOCBP are defined as any female who has experienced menarche, and who does not meet one of the following conditions:

- Postmenopausal: 12 months of spontaneous amenorrhea in females > 55 years of age or, in females ≤ 55 years, 12 months of spontaneous amenorrhea without an alternative medical cause and FSH levels in the postmenopausal range for the laboratory involved
- 6 weeks after surgical bilateral oophorectomy with or without hysterectomy
- Post hysterectomy

For the purposes of the study, highly effective contraception is defined as follows:

For male subjects:

- Highly effective male contraception includes a vasectomy with negative semen analysis at follow-up, or the non-pregnant female partner of WOCBP uses a highly effective contraceptive method (defined below)
- Male subjects with partners that are pregnant must use condoms as contraception to ensure that the fetus is not exposed to the Study Drug

For female subjects and female partners of male subjects, highly effective female contraception methods comprise:

- Surgical sterilization (e.g., bilateral tubal occlusion), hormonal contraception associated with inhibition of ovulation (combined estrogen and progestogen containing, or progestogen-only), intrauterine contraception device or intrauterine hormone-releasing system (IUS)

†Note: True abstinence (i.e., refraining from heterosexual intercourse throughout the duration of study participation) is only acceptable. Periodic abstinence (e.g., calendar, ovulation, symptothermal, post-ovulation methods), declaration of abstinence for the duration of a trial and withdrawal are not acceptable methods of contraception.

Note: A female condom and a male condom should not be used together as friction between the 2 can result in either or both products failing.

6.3.2. Other Requirements

Subjects must refrain from strenuous exercise/activity (e.g., heavy lifting, weight training, intense aerobics classes etc.) for at least 24 hrs prior to study visits.

All subjects will be required to fast for at least 8 hours before visits requiring fasted blood sampling.

7. STUDY DRUG

7.1. Study Drug Description

Study Drug (ISIS 757456 or Placebo) characteristics are listed in [Table 3](#).

The Study Drug (ISIS 757456 or placebo) is contained in 2-mL stoppered glass vials. The Study Drug (ISIS 757456 or placebo) and its storage and preparation instructions will be provided by the Sponsor or designee. The Study Drug (ISIS 757456 or placebo) must be stored securely at 2–8 °Celsius and be protected from light.

Table 3: Study Drug Characteristics

Study Drug	ISIS 757456	Placebo
Strength	100 mg/ mL	Not Applicable
Volume/Formulation	0.80 mL solution per vial	0.80 mL solution per vial
Route of Administration	SC	SC

7.2. Packaging and Labeling

The Sponsor will provide the Investigator with packaged Study Drug (ISIS 757456 or placebo) labeled in accordance with specific country regulatory requirements.

7.3. Study Drug Accountability

The study staff is required to document the receipt, dispensing, and return/destruction of Study Drug (ISIS 757456 or Placebo) supplies provided by the Sponsor according to Sponsor instruction and in accordance with institutional policy.

8. TREATMENT OF SUBJECTS

8.1. Study Drug Administration

Blinded vials of Study Drug will be provided by the Sponsor. Vials are for single use only. Study staff blinded to the identity of the drug will administer the Study Drug. Doses of 80 mg will be administered as a single SC injection at the Study Center. Volume to be administered is shown in [Table 4](#). Please refer to the Study Drug Manual provided by the Sponsor for more detailed instructions for Study Drug (ISIS 757456 or placebo) preparation and administration.

Table 4: Study Drug Dosing Information

Volume to Administer	Total Dose
0.80 mL	80 mg or placebo

8.2. Other Protocol-Required Drugs

There are no other protocol-required drugs concurrent with the Study Drug.

8.3. Other Protocol-Required Treatment Procedures

There are no other protocol-required treatment procedures.

8.4. Treatment Precautions

There are no treatment precautions required.

8.5. Safety Monitoring Rules

Please refer also to the 'Guidance for Investigator' section of the ISIS 757456 Investigator's Brochure.

In addition to the standard monitoring of clinical safety parameters, the following guidelines are provided for the monitoring of selected parameters chosen based on preclinical and clinical observations.

Confirmation Guidance: At any time during the Study (Treatment or Post-Treatment Periods), the initial clinical laboratory results meeting the safety monitoring criteria presented below must be confirmed by performing measurements (ideally in the same laboratory that performed the initial measurement) on new specimens. All new specimen collections should take place as soon as possible (ideally within 3 days of the initial collection). For stopping rules, if the initial laboratory result is observed during the Treatment Period, the results from the retest must be available prior to administering the next dose of Study Drug (ISIS 757456 or placebo).

Re-dosing Guidance: Subjects with initial laboratory test values that reach a stopping rule must not be re-dosed until the re-test results are available. In general, subjects who do not meet the stopping rules based upon retest may continue dosing. However, the Investigator and the Sponsor Medical Monitor (or appropriately qualified designee) should confer as to whether additional close monitoring of the subject is appropriate. If any of the stopping criteria described below (refer to Section 8.6.1 to Section 8.6.5) are met, the subject will be permanently discontinued from further treatment with Study Drug (ISIS 757456 or placebo), evaluated fully as outlined below and in consultation with the Sponsor Medical Monitor or appropriately qualified designee, and will be followed-up in accordance with Section 8.8.

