8.6. Stopping Rules

For the purposes of the stopping rules, Baseline is defined as:

- Temporary stopping rules for renal function tests – Baseline is defined as the last non-missing measurement prior to the first dose
- Stopping rules for platelets – Baseline is defined as the defined as the last non-missing measurement prior to the first dose

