8.6.3. Stopping Rule for Platelet Count Results

In the event of any platelet count less than 75,000/mm³, monitoring frequency and dosing should be adjusted as recommended in the table below.

Table 6: Actions in Patients with Low Platelet Count

Confirmed Platelet Count	Dosing	AESI?	Monitoring
$\geq 75,000/\text{mm}^3$	Yes	No	
 Monitor weekly
$< 75,000/\text{mm}^3$ to $50,000/\text{mm}^3$, in the absence of major bleeding or clinically-relevant non-major bleeding (defined below)	Pause	No	
 Monitor at least twice per week until 3 successive values above $75,000/\text{mm}^3$. Then monitor weekly until values normalize. The suitability of the patient for continued dosing will be determined by the Investigator in consultation with the Study Medical Monitor and will be based on factors such as the original rate of decline in the patient's platelet count, whether any bleeding events were experienced, and the speed of recovery of platelet count after interruption of dosing. The patient must have 3 successive values above $100,000/\text{mm}^3$ before continued dosing is considered. Perform additional labs in Table 5
$< 50,000/\text{mm}^3$ to $25,000/\text{mm}^3$	Permanently Discontinue	Yes, if only accompanied by a major bleeding event or CRNMB event, subject to 15-day expedited reporting	
 Monitor at least twice per week until 3 successive values above $75,000/\text{mm}^3$. Then monitor weekly until values normalize. A hematologist consultation may be considered at the discretion of the Investigator and Study Medical Monitor Perform additional labs in Table 5
$< 25,000/\text{mm}^3$	Permanently Discontinue	Yes, subject to 15-day expedited reporting	
 Monitor daily until 2 successive values above $25,000/\text{mm}^3$. Then monitor twice per week until 3 successive values above $75,000/\text{mm}^3$. Then monitor weekly until values normalize. Administration of steroids* and a hematologist consultation is recommended Perform additional labs in Table 5

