8.6.5. Stopping Rule for Blood Pressure

1. In the event of a SBP ≤ 90 mmHg with symptoms of hypotension (i.e., dizziness, light-headedness, clammy skin, fatigue, blurry vision), as measured by home BPM, at any point in the study, the patient should contact the Study Center immediately and have the SBP confirmed by the Study Center. If confirmed and the patient remains symptomatic, dosing of a subject with Study Drug will be interrupted. If patient is still symptomatic after instituting IV hydration (see Section 8.5.3 Safety Monitoring Rules for Blood Pressure), the patient should be admitted to the hospital. Timing for re-institution should be assessed depending on the reversibility of initiating factors (decreased oral intake, cold/flu, other illness). If the subject remains symptomatic Study Drug should be stopped permanently. If this occurs in the follow-up period, any other antihypertensives or other medications that could affect BP should be stopped, if feasible. The use of IV angiotensin II or vasopressors should be considered in subjects that remain symptomatic and are hemodynamically unstable. The subject will continue to be followed per protocol

in the study. Follow-up for subjects that screen fail due to blood pressure inclusion criteria (see Section 5.1) will not be necessary.

2. During the Treatment Period, should a subject experience a BP measurement > 170 mmHg (systolic) or > 110 mmHg (diastolic) a second measurement must be done within a 30-minute period. If the subject's BP is >170 mmHg (systolic) or > 110 mmHg (diastolic) within the 30-minute period, an additional BP measurement should be taken within 48 hours at the Study Center, regardless of whether the initial BP measurements were taken in clinic or at home. If the subject then experiences a BP measurement > 170 mmHg (systolic) or > 110 mmHg (diastolic) (confirmed by triplicate measurement at the Study Center), they will then be withdrawn from further blinded, randomized treatment. The subject's pre-study antihypertensive medication(s) may be added back per Investigator and Sponsor Medical Monitor judgement. The subject will continue to be followed per protocol in the study.

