8.8. Discontinuation of Study Drug

A subject must permanently discontinue study treatment for any of the following:

- The subject withdraws consent
- The subject experiences an AE that necessitates permanent discontinuation of Study Drug
- The subject develops laboratory test abnormalities that meet any of the stopping rules listed in Section 8.6.1 to Section 8.6.3
- The subject experiences an AE that necessitates unblinding of the Investigator to the subject's treatment assignment

The reason for discontinuation of Study Drug treatment must be recorded in the electronic Case Report Form (eCRF) and source documentation.

For subjects withdrawn for reasons other than withdrawal of consent every effort should be made to complete the early termination study procedures and observations at the time of withdrawal (see [Appendix A](#)) and ideally within 2 weeks from the last dose of Study Drug.

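### Section 8.5 makes every stopping criterion permanent, but Table 6 and the hypotension rule allow re-dosing, and Table 6 has no row for platelets of 50,000 to <75,000/mm³ with bleeding

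*Combined protocol and SAP*

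**What the plan says.** The general rule is in protocol section 8.5: once any criterion in 8.6.1 to 8.6.5 is met, "the subject will be permanently discontinued from further treatment with Study Drug (ISIS 757456 or placebo"). It states no exception.

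Section 8.6.3 then sets platelet actions by band. For any count below 75,000/mm³, "monitoring frequency and dosing should be adjusted as recommended in the table below". In Table 6 the row for <75,000 to 50,000/mm³ has the dosing entry *Pause* and applies "in the absence of major bleeding or clinically-relevant non-major bleeding (defined below"). It leaves a restart open: "The suitability of the patient for continued dosing will be determined by the Investigator in consultation with the Study Medical Monitor", once three successive values exceed 100,000/mm³. The rows below 50,000/mm³ all call for permanent discontinuation.

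Section 8.6.5 item 1 (systolic pressure of 90 mmHg or less with symptoms) begins with an interruption and continues: "Timing for re-institution should be assessed depending on the reversibility of initiating factors". It moves to a permanent stop only if symptoms remain.

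Section 8.8 requires permanent discontinuation for laboratory abnormalities that "meet any of the stopping rules listed in Section 8.6.1 to Section 8.6.3". Section 8.6 introduces its baseline definitions with the label "Temporary stopping rules for renal function tests", whereas 8.6.2 makes the renal stop permanent.

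**The concern.** A stopping rule should give one action for one finding. Here a site that reads 8.5 or 8.8 ends dosing for good at a confirmed count of, say, 60,000/mm³ without bleeding. A site that reads Table 6 holds the dose and may resume. Symptomatic hypotension raises the same question between 8.5 and 8.6.5 item 1. For the same platelet band with major or clinically relevant non-major bleeding, the table gives no instruction.

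What is mainly at stake is consistent safety conduct across the centres of a multi-centre trial, in the area that Amendment 1 set out to detail. The classification also matters for 8.7, which permits downward dose adjustment only where no stopping rule has been met. A secondary effect is on the analysis: the primary comparison is made in the Per Protocol Set (PPS), which requires at least 5 of the 7 doses, so ending or pausing treatment can decide membership.

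**Working it through.** **Text comparison.** The documents state no figure to reproduce here, so the provisions are set side by side.

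| Provision | Action in its own section | Action under 8.5 | In the laboratory item of 8.8? | Result |
|---|---|---|---|---|
| 8.6.1 liver | permanent | permanent | yes | consistent |
| 8.6.2 renal | permanent | permanent | yes | consistent, apart from the label in 8.6 |
| 8.6.3, <50,000/mm³ | permanent | permanent | yes | consistent |
| 8.6.3, <75,000 to 50,000/mm³, no major or clinically relevant non-major bleeding | pause, restart possible | permanent | yes | contradiction |
| 8.6.3, same band with such bleeding | no row | not determinable | not determinable | gap |
| 8.6.4 potassium | permanent | permanent | no | same action; cross-reference slip |
| 8.6.5 item 1 | interrupt, restart possible | permanent | not a laboratory rule | contradiction |
| 8.6.5 item 2 | withdrawn from randomized treatment | permanent | not a laboratory rule | consistent |

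The gap is not filled elsewhere. Section 8.5.4 requires the Table 5 work-up for any count below 75,000/mm³, but for the rule itself it refers to 8.6.3. Section 8.5.5 covers minor bleeding only. The adverse-event item in 8.8 is a case-by-case judgement.

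**Effect on the PPS.** Inputs: at least 5 of 7 doses for the PPS (protocol 10.3, SAP 3.3.1); primary analysis in the PPS (protocol 10.6.3, SAP 3.5.1); doses on Days 1, 3, 8, 15, 22, 29 and 36 (protocol 3.4.3). Assumption: missed doses are not made up after Day 36.

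Let the finding follow dose k (k = 1 to 6) and let a pause miss m doses (m = 1 to 7 − k, the last meaning no restart).

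- Permanent stop: doses received = k. In the PPS only if k ≥ 5, that is, from Day 22.
- Pause: doses received = 7 − m. In the PPS only if m ≤ 2.
- The two readings differ only when k ≤ 4 and m ≤ 2: 4 × 2 = 8 of the 6 + 5 + 4 + 3 + 2 + 1 = 21 combinations. This is a count of cases, not a probability.

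Example: the finding comes after the Day 8 dose, Days 15 and 22 are missed, and dosing resumes on Days 29 and 36. The pause gives 7 − 2 = 5 doses (in); a permanent stop gives 3 (out).

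**Effect on precision.** About 30 subjects at 2:1 gives a nominal 20:10. With equal variances, the standard error of the difference is proportional to √(1/n_active + 1/n_placebo).

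| PPS size (active:placebo) | Factor | Increase |
|---|---|---|
| 20:10 | 0.3873 | – |
| 19:10 | 0.3907 | 0.9% |
| 18:10 | 0.3944 | 1.8% |
| 20:9 | 0.4014 | 3.6% |
| 20:8 | 0.4183 | 8.0% |

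**The case against.** The best defence is that a specific provision overrides a general one. Table 6 names an action per band, 8.5.4 refers to the provision below 75,000/mm³ as a monitoring rule, the Amendment 1 summary describes the pause in the same terms, and 8.6.5 item 1 sets out an explicit sequence. A site that opens only the section for its parameter finds one answer. This makes the intent easier to guess, but it does not remove the conflict: the pause sits under a stopping-rule heading, and neither 8.5 nor 8.8 makes an exception for it. Nor does it supply the missing row.

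Several stronger readings are tempting, and the documents do not support them.

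- *Blood pressure is wrongly missing from 8.8.* The item covers laboratory abnormalities, and blood pressure is not one. Section 8.6.5 states its own stops.
- *The renal rules give sites two dosing rules.* The label in 8.6 introduces a baseline definition and carries no dosing instruction. No passage sets out a temporary stop with a restart for the 8.6.2 criteria; the discretionary hold there concerns lesser changes.
- *Leaving potassium out of 8.8 changes what happens.* It does not, because 8.5 and 8.6.4 both require a permanent stop.
- *A count of 50,000 to <75,000/mm³ with bleeding is wholly unmanaged.* The Table 5 work-up applies, and 8.8 allows discontinuation on judgement. What is missing is a stated dosing action and a monitoring schedule for that case.
- *The primary analysis is seriously exposed.* The conditions are narrow, and for platelets the requirement of three successive values above 100,000/mm³ makes a short pause less likely. Angiotensinogen at each scheduled visit, including Day 43, is also compared in the Full Analysis Set.

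**Conclusion.** The point stands as an internal inconsistency with two contradictions (8.5 and 8.8 against the *Pause* row of Table 6; 8.5 against 8.6.5 item 1) and one gap in Table 6. The renal label in 8.6 and the absence of potassium from the laboratory item in 8.8 are minor wording matters that change no action.

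The weight lies in safety conduct. The analysis effect is secondary: only the PPS dose criterion is touched, and only under the two conditions shown. Entry to the Full Analysis Set and the Safety Set does not depend on the number of doses. The precision figures rest on a nominal 20:10 split and equal variances. The documents give no expected frequency for these findings, so the overall effect cannot be quantified, but it is likely small unless such findings are common. The text should be corrected; this does not call the design into question.

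**What to change.** Reconcile 8.5, 8.6.3, 8.6.5 item 1 and 8.8 so that each criterion carries one stated action, either a hold with its restart condition or a permanent stop. Complete Table 6 so that every count below 75,000/mm³, with and without major or clinically relevant non-major bleeding, has a row giving dosing and monitoring. Correct the renal label in 8.6 and add 8.6.4 to the cross-reference in 8.8. Which clinical action applies is for the sponsor to decide.

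The cost is protocol wording in one amendment, with no added visits or procedures. The PPS definition needs no change on this account.
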